**Table 4: ME-401 Toxicity Management (Continued)**

Toxicity	Grade*	Management of ME-401	Management of Toxicity
	≥3	
 
Permanently discontinue ME-401.
 
	
 
Treat per institutional standard of care, including systemic corticosteroids.
 

Lung Infection/ Pneumonia	2	
 
Holding ME-401 is not required. Continue ME-401.
 
Dosing may continue at 60 mg administered on the IS.
 
	
 
Treat per institutional standard of care.
 

	3	
 
Hold ME-401 until AE resolved to Grade ≤1 or baseline.
 
Resume ME-401 at 60 mg administered on the IS.
 
Discontinue if same event occurs a third time.
 
	
 
Treat per institutional standard of care.
 

	4	
 
Permanently discontinue ME-401.
 
	
 
Treat per institutional standard of care.
 

Cytomegalovirus (CMV)	Any	
 
If test is positive (PCR or antigen assessment) based on local laboratory assessments and requires treatment, then hold ME-401 until recovery.
 
Resume ME-401 on the IS after resolution of asymptomatic CMV reactivation if all the following conditions are met: 
 
CMV reactivation is resolved per the Investigator assessment
 
 
 
CMV reactivation was not associated with end organ disease (e.g., pneumonia, hepatitis, gastroenteritis, retinitis, encephalitis).
 
	
 
Treat per institutional standard of care.
 
If all conditions for restarting study drug are met, then secondary CMV prophylaxis must be maintained as per institutional guidelines.
 

Hematological Toxicity	3	
 
Grade 3 neutropenia, febrile neutropenia or thrombocytopenia: ME-401 dosing may continue.
 
	
 
Perform CBC weekly until resolves to Grade ≤2 (unless myelosuppression is due to follicular lymphoma).
 

	4	
 
Grade 4 thrombocytopenia or Grade 4 neutropenia or febrile neutropenia: Hold ME-401 until AE resolves to Grade ≤3. Resume ME-401 at 60 mg administered on the IS.
 
	
 
Perform CBC weekly until resolves to Grade <3.
 

**Table 4: ME-401 Toxicity Management (Continued)**

Toxicity	Grade*	Management of ME-401	Management of Toxicity
		
 
Grade 4 neutropenia without associated symptoms: ME-401 therapy may continue. If symptoms persist despite adequate supportive care, ME-401 should be held until toxicity resolves to Grade <math>\leq 1</math> or baseline values and then ME-401 may be resumed at 60 mg administered on the IS.
 
	
 
Initiate growth factor support if clinically indicated. If subject is receiving filgrastim support or equivalent, CBC should be repeated after 3 days. Weekly CBCs should continue until resolves to Grade <math>< 3</math>.
 

		
 
Grade 4 thrombocytopenia without associated symptoms, ME-401 therapy may continue if Investigator deems safe.
 
	
 
Check platelets every 3 days until resolves to Grade <math>< 3</math>.
 

Other, not listed above, that are considered related to ME-401	2	
 
Holding ME-401 is not required. Continue ME-401.
 
Dosing may continue at the current dose or at 60 mg administered on the IS.
 
	
 
Treat per institutional standard of care.
 

	3a	
 
Hold ME-401 until AE resolves to Grade <math>\leq 1</math> or baseline.
 
Resume ME-401 at 60 mg administered on the IS.
 
For recurrence of the same Grade 3, permanently discontinue ME-401.
 
	
 
Treat per institutional standard of care.
 

	4	
 
Permanently discontinue ME-401.
 
	
 
Treat per institutional standard of care.
 

Abbreviations: AE = adverse event; ALT = alanine aminotransferase; AST = aspartate aminotransferase; CBC = complete blood count; CMV = cytomegalovirus; CT = computed tomography; CTCAE = Common Terminology Criteria for Adverse Events; IS = intermittent schedule; IV = intravenous; NIP = non-infectious pneumonitis; PCR = polymerase chain reaction; TENS = toxic epidermal necrolysis syndrome; ULN = upper limit of normal.

\* Toxicity graded per CTCAE v5.0.

Hy's law is defined as: cases of drug-related hepatocellular injury are defined as elevated ALT or AST  $\geq 3 \times$  ULN, plus elevated total bilirubin  $> 2 \times$  ULN without findings of cholestasis (defined as serum alkaline phosphatase [ALP] activity  $< 2 \times$  ULN), and no other reason can be found to explain.

a For Grade 3 AEs not related to study drug, it is upon the discretion of the Investigator if holding ME-401 is warranted. Treatment interruption must be discussed with the Sponsor's Medical Monitor or designee in such cases.

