### 5.3.1. Modified Dosing Schedules

Modification of the dosing schedule and dosing interruptions are utilized for toxicity management in this study. For subjects who experience toxicity during the first 2 cycles while receiving daily therapy with ME-401, dose interruption followed by a switch to intermittent schedule daily dosing for the first 7 days of every 28-day cycle is allowed. Subjects who experience toxicities on the IS will be managed by the instructions for management of potential drug-related toxicity in [Table 4](#), which may include dose interruption or permanent discontinuation of ME-401. All treatment interruptions (including any missed doses, treatment delays) and discontinuations and their reasons are to be recorded in the electronic case report form (eCRF). Interrupted treatment is resumed on the IS after subjects recover to the grade specified in the table (subjects who permanently discontinue ME-401 dosing will proceed to the EOT/30-Day Safety Follow-up visit). Subjects on the IS who recover within the same treatment cycle, will complete the planned days off, and resume treatment on Day 1 of the next planned cycle.

Subjects who interrupt study drug dosing for  $>6$  continuous weeks will have ME-401 permanently discontinued unless restarting ME-401 is authorized by the study Medical Monitor. Consultation with the Sponsor's Medical Monitor or designee is recommended before treatment interruption or discontinuation due to any reason.

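### Protocol Table 4 gives both a hold and a continue instruction for asymptomatic Grade 4 neutropenia and thrombocytopenia and, for neutropenia only, two restart grades

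*Protocol*

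**What the plan says.** The Hematological Toxicity part of Protocol Table 4 has one Grade 4 row, which runs over a page break and holds three entries on study drug.

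- **General entry:** "Grade 4 thrombocytopenia or Grade 4 neutropenia or febrile neutropenia: Hold ME-401 until AE resolves to Grade ≤3". Dosing then resumes on the intermittent schedule.
- **Neutropenia entry:** "Grade 4 neutropenia without associated symptoms: ME-401 therapy may continue". It goes on: "If symptoms persist despite adequate supportive care, ME-401 should be held until toxicity resolves to Grade" ≤1 "or baseline values and then ME-401 may be resumed at 60 mg administered on the IS".
- **Thrombocytopenia entry:** "Grade 4 thrombocytopenia without associated symptoms, ME-401 therapy may continue if Investigator deems safe". It names no recovery grade.

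The Grade 3 row just above reads: "Grade 3 neutropenia, febrile neutropenia or thrombocytopenia: ME-401 dosing may continue".

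Section 5.3.1 makes the table govern restart: "Interrupted treatment is resumed on the IS after subjects recover to the grade specified in the table".

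**The concern.** The general entry is not limited to symptomatic cases, so it covers the asymptomatic counts that the two later entries let through. A site that reads the first line stops the drug; a site that reads on may continue it. For neutropenia there is a second problem: once drug is held, the row contains two different recovery grades.

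The first thing at stake is consistent handling of a Grade 4 laboratory finding. The second is the exposure and safety data. SAP Section 8.1 summarizes interruptions due to AEs and relative dose intensity, Section 8.2 calculates compliance, and Section 8.3.3 tabulates TEAEs leading to interruption. If sites follow different lines, these summaries mix drug tolerability with the choice of line. Under Section 5.3.1, an interruption of more than 6 continuous weeks leads to permanent discontinuation unless the Medical Monitor authorizes restart, and discontinuation for toxicity is an event for time to treatment failure. A later restart grade could therefore reach that endpoint too.

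**Working it through.** No sample size, power or test is involved, so the check is a comparison of the entries case by case.

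| Grade 4 case | General entry | Specific entry |
|---|---|---|
| Neutropenia, no symptoms | Hold; restart at ≤3 | May continue |
| Thrombocytopenia, no symptoms | Hold; restart at ≤3 | May continue, if judged safe |
| Neutropenia, symptoms persisting despite supportive care | Hold; restart at ≤3 | Hold; restart at ≤1 or baseline |
| Thrombocytopenia with symptoms | Hold; restart at ≤3 | None |

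**Hold or continue.** The first two cases each carry two different instructions. Table 4 does mark exceptions elsewhere: the Grade 2 diarrhea/colitis and Grade 2 cutaneous entries each hold drug unless a stated condition is met. The Grade 4 hematological entries contain no such word.

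**Restart grade.** Only the third case has two recovery grades. Suppose the later entries are read as exceptions, so that the general entry covers symptomatic cases. The neutropenia entry is headed as applying without symptoms, yet its hold depends on symptoms persisting. A subject with persisting symptoms then meets the general entry (≤3) and also the hold clause of the specific entry (≤1 or baseline). Section 5.3.1 points back to the table and does not choose between them. For thrombocytopenia the only restart grade in the row is ≤3.

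**Size.** No figure is specific to Grade 4 neutropenia or thrombocytopenia.

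- Section 5.3 reports neutrophil count decreased at Grade ≥3 in 4 of 52 Phase 1b monotherapy subjects (4/52 = 7.7%). This can include Grade 3 events, for which dosing may continue.
- Section 1.6.2.1 reports a Grade 4 TEAE of any kind in 4 of 52 monotherapy subjects. Assuming both sections describe the same 52 subjects, Grade 4 neutropenia lies between 0/52 and 4/52, that is 0% to 7.7%. The range covers doses of 60, 120 and 180 mg, whereas this study gives 60 mg.
- Section 2.3 states that no Grade 4 toxicity had occurred on either schedule. Section 1.6.2.3 counts Grade 4 TEAEs in 3 of 47 subjects on continuous and 2 of 43 on intermittent dosing. The statement of none therefore cannot serve as a rate.

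**What one difference can do to exposure.** From Cycle 3, planned dosing is 7 × 60 mg = 420 mg per 28-day cycle, which agrees with the SAP's intended dose of (60/4) × 28 = 420 mg. Resumption is on Day 1 of a cycle. Assuming cycle dates do not shift, a recovery grade met before the next Day 1 under one criterion but only after it under the other changes that cycle's dose from 420 mg to 0 mg. If both criteria are met before Day 1, the dose does not change.

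**The case against.** The strongest answer is that the three entries form one block: a general rule followed by two narrower ones, each with its own monitoring instruction. On ordinary reading the specific entry qualifies the general one, and the later entries are permissive in wording. The missing piece may be a single word limiting the hold to symptomatic cases. This reading is reasonable and stands as a likely intention. It would settle the hold-or-continue question, but the text does not state it, and it leaves the two neutropenia restart grades in place.

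The practical effect may also be small. From Cycle 3 subjects are off drug for 21 of 28 days, consultation with the Medical Monitor is recommended before interruption, the exposure summaries are descriptive, and enrollment is closed. All of this stands and limits the size of the point. The consultation is recommended, not required, so it does not ensure uniform handling.

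Stronger readings are tempting but not supported:

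- **Two restart grades for thrombocytopenia as well.** Its specific entry gives none, so only Grade ≤3 applies.
- **An entry that starts more permissively and ends stricter is wrong in itself.** A different criterion for a narrower case is not an error. The fault is that the cases overlap.
- **The 7.7% measures the affected subjects.** It is a Grade ≥3 figure across Phase 1b doses, not a Grade 4 rate.
- **Febrile neutropenia is a further direct contradiction.** It is named in both the Grade 3 and Grade 4 rows, but the rows are divided by grade. Its scope in the Grade 4 entry merely needs to be made explicit.

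**Conclusion.** The point holds as an internal inconsistency in the current Table 4. As written, asymptomatic Grade 4 neutropenia and asymptomatic Grade 4 thrombocytopenia each meet both a hold and a continue instruction. A held Grade 4 neutropenia can fall under two restart grades. The hold-or-continue conflict rests on the general entry having no symptom qualifier and no text ranking the entries. The restart-grade conflict survives even if the later entries are accepted as exceptions.

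The number of subjects affected cannot be derived from the documents. The sample size and the primary ORR test are untouched. What is affected is subject safety and the comparability of interruption, dose-intensity and compliance data across sites. The correction should be made, but the point does not call the design into question.

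**What to change.** The sponsor should reconcile the Grade 4 hematological entries in Table 4. Each entry should state the cases it covers (neutropenia, febrile neutropenia or thrombocytopenia; with or without symptoms), and each case should have one instruction on study drug and one recovery criterion, so that the reference in Section 5.3.1 leads to a single grade. Which rule is right is for the sponsor to decide; none is proposed here.

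The cost is a table edit and its communication to sites. Because enrollment is closed, the edit serves subjects still on treatment. For events already recorded, the interruption reasons that Section 5.3.1 requires on the eCRF can be listed beside the Grade 4 counts, so that a reader of the exposure summaries can see how each was handled. That needs no new data collection.

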### 5.3.2. Adverse Events of Special Interest (AESIs)

In this study, the following are considered AESIs:

- Cutaneous reactions, including skin rash Grade  $\geq 2$  (see [Appendix 3](#) for guidance for toxicity assessment)
- Oral mucositis or stomatitis Grade  $\geq 2$
- Diarrhea/colitis Grade  $\geq 2$

- It is important to differentiate infectious diarrhea from non-infectious diarrhea, as treatment and management of subjects will depend on the identified cause (see [Table 4](#) for management of non-infectious diarrhea). To confirm suspected colitis, utilize colonoscopy or diagnostic methods as per institutional standards.
- AST/ALT Grade  $\geq 2$
- Non-infectious pneumonitis (NIP) of any grade
- Lung infection/pneumonia Grade  $\geq 2$
- Cardiomyopathy of any grade

Refer to [Table 4](#) for ME-401 Toxicity Management.

### 5.3.3. Other Potential Toxicities

#### 5.3.3.1. Phototoxicity

Based on neutral red uptake phototoxicity assay of ME-401 in BALB/c 3T3 mouse fibroblasts, ME-401 did not demonstrate phototoxic potential.

## 5.4. Monitoring and Prophylaxis of Opportunistic Infection

### 5.4.1. Monitoring for Opportunistic Infection

In addition to the clinical review and laboratory tests outlined in the Schedule of Assessments ([Appendix 1](#)), the following should be performed in all subjects prior to start of every cycle of treatment with ME-401:

- Evaluation of any new onset or worsening of pulmonary symptoms (i.e., cough, dyspnea, or fever) that includes a lung examination at each visit prior to treatment to rule out opportunistic infection (OI), including PJP *Pneumocystis jirovecii* pneumonia/PCP (*pneumocystis* pneumonia).
- Laboratory tests:
  - CD4 (for subjects with signs of infection)
  - Blood cultures if febrile neutropenia occurs, or when ANC by NCI CTCAE is Grade 4
  - PCR for CMV (every cycle for first 6 months of treatment and every 3 months thereafter). If PCR test is positive for CMV and treatment is initiated, then treatment with ME-401 should be delayed until recovery. Treatment of CMV should be initiated based on local SOC. Retreatment with ME-401 will be allowed on the IS once PCR test for CMV is negative. Please note: quantitative results from PCR measurements must be reported for all CMV assessments.

Implement enhanced monitoring prior to start of every cycle of treatment with ME-401 when prior medical history or laboratory parameters could be associated with one of the following risk factors:

- Intensive chemotherapy ( $\geq 2$  lines of myelosuppressive cytotoxic therapy)

- History of symptomatic CMV infection, systemic herpes
- History of lower respiratory tract infection
- History of immunodeficiency in the last 12 months (excluding lymphoma)
- Lymphocyte count  $<500/\text{mm}^3$  while on treatment in clinical study

For subjects with identified risk factors and those who developed an OI while on study treatment, additional assessments may include:

- CD4 and CD8 count and ratio, c-reactive protein, blood cultures
- Any additional laboratory and diagnostic methods according to local SOC reported as unscheduled laboratory and diagnostic methods of assessment
- Radiological imaging (i.e., chest X-ray or CT scans)
  - Note: Treatment of the OI that started while on study should be based on local SOC.

#### **5.4.2. Prophylaxis of OI Other Than PJP/PCP**

Mandatory prophylactic therapy is not mandated in all subjects for the following reasons:

- Mandatory prophylaxis may cause a higher risk of side effects associated with supportive treatment where no risk factors are present
- The current schedule of assessments and additional steps noted above provide frequent monitoring and flexibility for prophylaxis based on local SOC

Although not mandated in all subjects, OI prophylaxis may be initiated at the discretion of the treating Investigator's judgment of the risk-benefit ratio in any subject, irrespective of whether a high-risk feature is present. Treatment, dosage, and route of administration must be reported on the concomitant medication page of the eCRF.

Prophylactic treatment of OI should be initiated based on SOC in subjects when high risk factors are identified ([Section 5.4.1](#)).

#### **5.4.3. Prophylaxis of PJP/PCP**

Prophylaxis against PJP/PCP is mandatory; the preferred treatment is trimethoprim-sulfamethoxazole (TMP-SMX) option because of ease of administration and is typically achieved with one tablet (TMP 80 mg/SMX 400 mg) administered once or twice daily, 3 times/week on consecutive or alternate days. However, TMP/SMX is (1) a selective inhibitor of CYP2C8, a cytochrome P450 isoform that affects zandelisib metabolism, and (2) can be associated with myelosuppression, requiring a switch to an alternate option. If TMP-SMX is not tolerated, PJP prophylaxis with either atovaquone or aerosolized pentamidine is recommended. Because dapsone has been associated with methemoglobinemia in the zandelisib Phase 1b study, it should not be used for PJP prophylaxis.

The mandatory PJP prophylaxis should start within one week of starting zandelisib until the completion of 30-day safety follow up from the last dose of zandelisib treatment.

When Prophylaxis is used for OI and PJP, treatment, dosage, and route of administration must be reported on the concomitant medication page of the eCRF.

## 5.5. Prohibited Treatments and Cautions for Concomitant Medications

The following medications/therapies are **prohibited** during the study:

- Other investigational agents
- Cancer therapies not mentioned in this protocol
- Dapsone (for PJP prophylaxis)
- Drugs that are strong inhibitors/inducers of CYP3A4 ([Appendix 8](#))
- Systemic corticosteroids in doses >10 mg in prednisone equivalency are prohibited for one week prior to Cycle 1 Day 1 and during the study, except when used:
  - 1) for the treatment of an adverse reaction or other acute clinical situations
  - 2) for the treatment of an exacerbation of known chronic conditions

The following medications/therapies should be used **with caution**

- Drugs that are strong inhibitors/inducers of CYP2C8 ([Appendix 7](#)).
- Drugs that are known to prolong the QT/QTc interval should be used with caution ([Appendix 9](#))
- Orally administered drugs known to interact with drugs that inhibit the intestinal transporters BCRP and P-gp should be used with caution

Note: Palliative radiation therapy of non-curative intent is permitted on study **except** to target and non-target lesions.

## 5.6. Advisory on COVID-19 Vaccination, Management, and Risk Assessment

COVID-19 vaccination, where authorized or approved by national regulatory authorities, is recommended for patients who are currently enrolled in this study, in accordance with COVID-19 vaccination guidance from scientific and medical associations (e.g., [American Society of Hematology](#), [American Society of Clinical Oncology](#), [NCCN](#), and [European Hematology Association](#)).

The Sponsor completed a risk assessment for COVID-19 vaccination of patients while on study drug and concluded the benefit of receiving anti-lymphoma therapy for patients with R/R FL and MZL outweigh the potential risk of delaying treatment due to scheduled COVID-19 vaccination. Potential risks associated with COVID-19 vaccination while on study drug have not been fully established.

Vaccination is recommended, whether administered prior to enrollment or during study participation. Investigators are advised to adhere to local regulatory and institutional guidance for vaccination.

Information about vaccination should be recorded as a concomitant medication with the dates of each dose of vaccination.

If COVID-19 infection is confirmed, COVID-19 infection should be managed per local guidance until the subject recovers. In the event of a positive COVID-19 case, the investigator must determine the risk and benefit of interruption versus continuation of zandelisib. Zandelisib should be temporally interrupted. After the subject recovers from the COVID-19 event, zandelisib treatment should be resumed. Permanent discontinuation of study drug (if COVID-19 test is positive or if symptomatic COVID is diagnosed) must be discussed with the study medical monitor. If a subject is found to have a positive COVID-19 test, enter the COVID-19 results in the AE CRF page. Also, enter any AEs associated with COVID-19 infection in the AE CRF page.

### **5.7. Discontinuation of ME-401 Treatment**

Administration of ME-401 will continue unless one of the following occurs:

- Progressive disease, unless the Investigator deems a switch to continuous dosing is in the best interest of the subject and the subject agrees to continue treatment with CS dosing
- Unacceptable AE(s) considered related/possibly related to ME-401 despite appropriate therapy and modified dosing schedule
- Withdrawal of consent by the subject
- Changes in the subject's medical condition that render further administration of ME-401 unacceptable in the judgement of the Principal Investigator or Sponsor
- Non-compliance
- Termination of study by Sponsor

Subjects who discontinue from therapy should be followed for efficacy and survival unless they withdraw consent to participate.

### **5.8. Discontinuation of Subjects from Study**

Subjects may be discontinued from the study for any of the following reasons:

- Withdrawal of consent for further participation or follow-up
- Subject is lost to follow-up
- Termination of study by Sponsor

### **5.9. Site Discontinuation**

The Sponsor has the right to close a site at any time. Reasons for closing a site may include, but are not limited to, the following:

- Non-compliance with International Council for Harmonisation Good Clinical Practice (ICH-GCP) guidelines
- Inadequate rate of subject recruitment
- Poor protocol adherence
- Inaccurate or incomplete data recording

- No study activity (i.e., all subjects have completed, and all obligations have been fulfilled)

